#### Adverse Events

Adverse events (AEs) will be coded in MedDRA, version 14.0 or higher. Treatment-Emergent Adverse Event (TEAE) is defined as any AE occurs on or after applying the first dose of study drug. Number and percent of subjects reporting TEAEs will be tabulated by treatment group. Summaries will be presented by body system and preferred term for the ITT population. Similar tables will be presented by severity and relationship to study drug. TEAEs reported by 5% or more subjects for any treatment group will also be summarized. In summaries of incidence rates (frequencies and percentages), severity and relationship to study drug of individual, subjects who report more than one event that are mapped to the same preferred term will be counted only once under the strongest severity and relationship, accordingly. The difference between Test and Reference treatments with regard to the severity and frequency of their dermatological adverse events will be statistically evaluated. Fisher's exact test will be used to compare the proportions of subjects of the two active treatment groups who report any TEAE.

Treatment-Emergent Serious Adverse Events (TESAEs) and TEAEs that led to treatment interruption or discontinuation will be presented in data listings.

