7.2 Definitions

An adverse event (AE) is defined as any untoward medical occurrence in a subject administered a medicinal product and which does not necessarily have to have a causal relationship with this treatment. An adverse event can therefore be any unfavorable and unintended sign (for example, an abnormal laboratory finding), symptom, or disease temporally associated with the use of a medicinal product, whether or not considered related to this medicinal product.

A serious adverse event (SAE) is an adverse event that results in any of the following outcomes:

- death
- life-threatening event (i.e., the subject was, in the opinion of the investigator, at immediate risk of death from the event as it occurred. It does not include an event that, had it occurred in a more severe form, might have caused death)
- requires in-subject hospitalization or prolongs hospitalization
- a persistent or significant disability/incapacity or substantial disruption of the ability to conduct normal life functions
- congenital anomaly/birth defect
- Other adverse events that may be considered serious based upon appropriate medical judgment, may jeopardize the subject and may require medical or surgical intervention to prevent one of the outcomes listed above, e.g. allergic bronchospasm requiring intensive treatment in an emergency room or home, blood dyscrasias or convulsions that do not result in hospitalization, or the development of drug dependency or drug abuse

Immediately Reportable Adverse Events (IRAE): Any serious AE or any AE that necessitates discontinuation of study medication, including pregnancy.

Unexpected Adverse Event: An unexpected event is any adverse drug experience, the specificity or severity of which is not consistent with the current approved product labeling (package insert) for the study medication, the Investigator's Brochure, or as described in the clinical protocol and consent materials.

Intensity of Adverse Events: The maximum intensity of an AE during a day should be recorded on the CRF. If the intensity of an AE changes over a number of days, then separate entries should be made having distinct onset dates for the changes in severity.

Mild - AEs are usually transient, requiring no special treatment, and do not interfere with subject's daily activities.

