7.3 Eliciting and Reporting of Adverse Events

The investigator will periodically assess subjects for the occurrence of adverse events. In order to avoid bias in eliciting adverse events, the subject or parent/legally authorized representative should be asked a non-specific question (e.g., "How have you been feeling since your last visit?") to assess whether any AE has been experienced since the last visit. All adverse events (as defined in Section 7.2), either observed by the Investigator or one of his/her medical collaborators, or reported by the participant spontaneously, or in response to direct questioning, will be reported and documented in the source and the study reporting forms. When reporting an adverse event, the Investigator must assign a severity grade to each event and declare an opinion on the relatedness of the event to the study medication or procedure. Serious or unexpected adverse events must be reported to Perrigo **within 24 hours** of when the Investigator first learns of the occurrence of the event.

Adverse events will be documented in source and recorded in a timely manner on case report forms. Adverse events that are identified at the last assessment visit (or the early termination visit) must be recorded on the AE case report form (CRF) with the status of the AE noted.

Adverse event reporting begins from the signing of informed consent/assent. Adverse events should be followed until resolved or 30 days after the final study treatment. In any case, serious adverse events that are not resolved or considered to be chronic within 30 days of the final study treatment must be followed by the investigator until they become resolved or are considered to be chronic (stabilized for at least 30 days). All events that are ongoing at this time will be recorded as ongoing on the CRF.

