9. CONSENT/ASSENT CONSIDERATIONS AND PROCEDURES

It will be made clear to the subject that, for the purposes of the study, they are consenting only for topical application of medication or vehicle. Investigators may discuss the availability of the study and the possibility for entry with a potential subject without first obtaining consent/assent. However, informed consent/assent must be obtained and documented prior to initiation of any procedures that are performed solely for the purpose of determining eligibility for research, including withdrawal from current medication(s). When this is done in anticipation of, or in preparation for, the research, it is considered to be part of the research.

The study must be approved in writing by an appropriate IRB as defined by FDA regulations. A copy of the Letter of Approval from the IRB, which also contains specific identification of the documents approved, must be received by Perrigo Pharmaceuticals, prior to study commencement.

Periodic status reports must be submitted to the IRB at least annually as required by the site's IRB, as well as notification of completion of the study and a final report within three months of study completion or termination. A copy of all reports submitted to the IRB must be sent to Perrigo Pharmaceuticals.

The investigator(s) has both ethical and legal responsibility to ensure that each subject being considered for inclusion in this study is given a full explanation of the protocol. This shall be documented on a written informed consent/assent form, which shall be approved by the same Institutional Review Board (IRB) responsible for approval of this protocol. Each informed consent/assent form shall include the elements required by FDA regulations in 21 CFR Part 50. The investigator agrees to obtain approval from Perrigo Pharmaceuticals of any written informed consent/assent form used in the study, preferably prior to submission to the IRB.

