## 6 Appendices

### 6.1 Handling of Missing or Incomplete Dates for Adverse Events and Concomitant Medications

#### Adverse Events

Handling of partial dates is only considered for the start date. An adverse event with a partial start date is considered treatment emergent if:

- only the day is missing and the start month/year is the same or after the month/year of the first dose
- the day and month are missing and the start year is the same or greater than the year of the first dose date
- the start date is completely missing

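### Read entry by entry, the AE recording and TEAE rules count a pre-dose event that eases after first dose as treatment-emergent; the effect is probably very small and a one-line definition fixes it

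*SAP*

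**What the plan says.** Four rules bear on this point.

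- **Recording.** Protocol 7.2, under intensity of adverse events, says that when intensity changes over several days "separate entries should be made having distinct onset dates for the changes in severity". The rule is not limited to worsening.
- **Start of collection.** Protocol 7.3: "Adverse event reporting begins from the signing of informed consent/assent". Events before the first application therefore reach the CRF.
- **Definition.** SAP 5.6, Adverse Events: "Treatment-Emergent Adverse Event (TEAE) is defined as any AE occurs on or after applying the first dose of study drug".
- **Date used.** SAP 6.1, on incomplete AE dates: "Handling of partial dates is only considered for the start date". Treatment emergence is then decided by comparing that start date with the first dose.

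The TEAE flag feeds the SAP 5.6 tables of incidence, severity, relationship to study drug and events reached by 5% of an arm. It also feeds one test: "Fisher's exact test will be used to compare the proportions of subjects of the two active treatment groups who report any TEAE".

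**The concern.** A treatment-emergent flag is meant to pick out events that appear or get worse once treatment has started. Here the flag can depend on how an event was entered. Consider an illness that is moderate before the first application and mild shortly afterwards. It acquires a second entry dated after first dose, and that entry meets the SAP definition, although all that happened after dosing was improvement. Had the event stayed as one entry with its original start date, it would not have been flagged.

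What is at stake is the accuracy of the TEAE tables and of the Test versus Reference comparison of subjects with any TEAE. Events unrelated to treatment that are added to both arms raise both rates and bring them slightly closer. That is the less cautious direction when the hoped-for conclusion is comparable safety.

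**Working it through.** The documents give no figure to reproduce. The check has two parts: applying the rules to a mock event, and sizing the effect with assumed rates.

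**1. Applying the rules.** The mock event starts 2 days before first dose and changes intensity 1 day after it. SAP 5.6 leaves three readings open:

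| Reading of the TEAE definition | Moderate, then mild after dose | Mild, then moderate after dose |
|---|---|---|
| Each entry judged on its own onset date | counted (mild TEAE) | counted (moderate TEAE) |
| Event judged on its original onset date | not counted | not counted |
| Event counted if still present after dose | counted | counted |

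The first reading follows from the separate onset dates in Protocol 7.2 and the start-date rule in SAP 6.1. It handles worsening correctly and easing wrongly. The second handles easing correctly but misses genuine worsening. The third counts both. None handles both directions as intended.

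**2. Whether another rule repairs it.** SAP 5.6 says that "subjects who report more than one event that are mapped to the same preferred term will be counted only once under the strongest severity and" strongest relationship. This removes duplicates among the TEAEs within a preferred term. The pre-dose entry is not a TEAE, so the easing entry is the only one left and is tabulated. No readable text links split entries or compares post-dose with pre-dose intensity.

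**3. Whether a pre-dose interval can exist.** Protocol 9 says that "informed consent/assent must be obtained and documented prior to initiation of any procedures that are performed solely for the purpose of determining eligibility for research", and it includes stopping current medication among these procedures. The same section refers to a screening phase and to re-screening. Against this, the visit schedule starts at Visit 1/Day 1 (Baseline), and Protocol 5.11 places the first application on Day 1 at the site. A gap is allowed for, but its length is not visible.

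**4. Size.** Let p be the true proportion of subjects with any TEAE. Let q be the proportion with a pre-dose AE that eases after dosing, taken as independent of having a true TEAE. Both are assumed.

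Reported rate = p + (1 − p)q

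- p = 20%, q = 0.5%: 0.20 + 0.80 × 0.005 = 0.204, or 20.4%
- p = 20%, q = 2%: 0.20 + 0.80 × 0.02 = 0.216, or 21.6%
- p = 10%, q = 0.5% to 2%: 10.45% to 11.8%
- p = 40%, q = 0.5% to 2%: 40.3% to 41.2%

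With the same q in both arms, the reported difference is

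[p_T + (1 − p_T)q] − [p_R + (1 − p_R)q] = (p_T − p_R)(1 − q)

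For an illustrative 25% versus 20%, the 5.0-point difference becomes 5.0 × 0.995 = 4.975 points at q = 0.5%, and 5.0 × 0.98 = 4.90 points at q = 2%. The loss is 0.025 to 0.10 of a percentage point.

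**The case against.** The strongest reply is that an entry is not an event. Protocol 7.2 speaks of the intensity of one AE changing and of several entries for it, while SAP 5.6 defines a TEAE as an AE, not as an entry. An analyst could therefore keep the original onset and not flag the easing event. That reading is possible, but neither document states it. The separate onset dates and the start-date rule point the other way, and the reading would also drop true worsening. The ambiguity therefore stands and needs settling.

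The second reply is that there may be little opportunity for the error. If consent, baseline and first application fall on the same day, q is close to zero. Protocol 7.2 also defines an AE as arising in a subject who has been given a medicinal product. Because Protocol 7.3 starts collection at consent, this does not keep earlier events off the CRF, but it adds doubt about how many there would be. This reply stands as a limit on size.

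Third, Protocol 5.10 keeps most application site reactions out of the AE data unless they lead to interruption, discontinuation or new medication. SAP 5.6 summarizes them separately by visit, so the TEAE flag does not touch those summaries. This also stands.

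A reader might infer that the Test-Reference difference falls by 0.5 to 2 percentage points, or that the arms are materially pulled together. The arithmetic does not support that: the shrinkage is a relative factor of (1 − q). A reader might also take the Fisher test to be the only planned safety comparison. It is the only safety test that the SAP names, but SAP 5.6 also promises a statistical evaluation of dermatological AEs, without naming the method.

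**Conclusion.** The concern holds as a small defect of definition. Under an entry-level reading, which the texts favor but do not state outright, an AE that starts between consent and first dose and eases afterwards is counted as a TEAE. No readable section corrects this.

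The size depends on p and q, neither of which is in the documents, and on a consent-to-dose interval whose length cannot be seen. On the assumed values the any-TEAE rate rises by 0.4 to 1.6 points from 20%. Under blinded randomization the error should be non-differential, so it favors neither product, and the Fisher result is unlikely to change. Efficacy equivalence and superiority do not depend on the flag.

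It would be tempting to conclude that the trial's safety comparison is biased, or that misclassified events are known to occur. The documents support neither conclusion: they schedule no separate screening visit, and they give no count of pre-dose events. The priority is low. The change is worth making because it costs almost nothing.

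**What to change.** In SAP 5.6, replace the definition with one that counts an AE as treatment-emergent if either of these holds:

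- it is new on or after first dose;
- its intensity on or after first dose is higher than its last pre-dose intensity.

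Add that split entries of one event, identified by the same term and adjoining dates, keep the original onset date for this purpose. The easing event then gives no TEAE, the worsening event still gives one, and the any-TEAE proportion returns from p + (1 − p)q to p.

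The cost is one or two sentences in the SAP and a small amount of programming to join the entries. No CRF change is needed. Protocol 8 requires the SAP to be final before the blind is broken, so the change should be made by then.

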5.10 Application Site Reaction Assessment

At baseline and each subsequent visit, application site reactions such as erythema, dryness, burning/stinging, erosion, edema, pain and itching are to be recorded. Pain and itching symptoms will be assessed by discussion with the subject and will be reported as the severity experienced within 24 hours of the trial visit.

The Application Site Reaction Assessment must be conducted by qualified investigators listed on the Form FDA 1572 who have been delegated these tasks by the PI. [REDACTED]

[REDACTED]

[REDACTED]

Application site reactions are not to be recorded as adverse events unless they result in either:

- The temporary discontinuation of the study medication.
- The discontinuation of the subject from the study.
- The use of a new concomitant medication in order to treat this event.

Site Reaction	DESCRIPTION
Erythema	[REDACTED]
Dryness	[REDACTED]
Burning/Stinging	[REDACTED]
Erosion	[REDACTED]
Edema	[REDACTED]
Pain	[REDACTED]
Itching	[REDACTED]

SCORE	ASSESSMENT	DESCRIPTION
0	None	Absent
1	Mild	Slight, barely perceptible
2	Moderate	Distinct presence
3	Severe	Marked, intense

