8.1.5 Safety and Adverse Events Analysis

The frequency and percent of subjects with adverse events will be summarized by MedDRA system organ class and preferred term and by severity and relationship to study drug for all three treatment groups. The adverse events reported by at least five percent of the subjects in any treatment group will also be tabulated. The comparable safety of the Test and Reference

[REDACTED]

treatments will be evaluated by statistical comparison of the proportion of subjects who reported any adverse events. The test and reference treatments' frequency and distribution of application site reactions of erythema, burning/stinging, erosion, edema, pain and itching will be summarized and compared descriptively. Safety comparisons will be performed only for the safety intent-to-treat population.

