#### Application Site Reactions

Frequency and distribution of application site reactions of erythema, dryness, burning/stinging, erosion, edema, pain and itching will be summarized and compared descriptively by visit.

Safety comparisons will be performed only for the ITT population.

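### The only visible formal skin-specific comparison of Test with Reference leaves out local reactions that needed no action, so its power for a tolerability difference may be reduced

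*SAP*

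**What the plan says.** Comparing the safety profiles of the two gels is a stated objective (Protocol 2, SAP 2). Local reactions are recorded in two places.

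- **Scores.** Protocol 5.10: "At baseline and each subsequent visit, application site reactions such as erythema, dryness, burning/stinging, erosion, edema, pain and itching are to be recorded". Each is graded 0 (none) to 3 (severe).
- **AE data.** The same section: "Application site reactions are not to be recorded as adverse events unless they result in either" of three outcomes. These are a temporary stop of study medication, discontinuation from the study, or "The use of a new concomitant medication in order to treat this event".

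The planned analyses are:

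- SAP 5.6, Adverse Events: the Test-Reference difference "with regard to the severity and frequency of their dermatological adverse events will be statistically evaluated". No test is named, and no list of terms defines which AEs count as dermatological.
- The same paragraph: "Fisher's exact test will be used to compare the proportions of subjects of the two active treatment groups who report any TEAE". This is not specific to skin and draws on the same AE data.
- SAP 5.6, Application Site Reactions: the scored signs "will be summarized and compared descriptively by visit". The protocol synopsis and Protocol 8.1.5 also plan description only. The list in 8.1.5 omits dryness, which the synopsis and the SAP include.

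Protocol 7.3 asks for all AEs as defined in 7.2 to be reported and does not repeat the exception in 5.10.

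**The concern.** Protocol section 7 names cutaneous irritation as the treatment-related reaction to the reference product, so local tolerability is an obvious place to look for a difference between two gels. The plan commits to a formal comparison there but runs it on the AE data. A local reaction enters those data only if someone acted on it, so entry reflects how the subject and site responded as well as the reaction itself. A comparison of severity within that set is also conditional on action having been taken.

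The scores do not depend on action, but they get only by-visit tables. Such tables do not show how many subjects ever had a moderate or severe reaction. The visible text also does not say how scores from early-termination or unscheduled visits enter them.

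At stake is the reading of a null result. A non-significant comparison of dermatological AEs could be reported as comparable skin tolerability, although local reactions that needed no action were never in it.

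**Working it through.** The plan has no figure to reproduce: sample size and allocation are redacted, and no power is shown for any safety comparison. What follows is a sensitivity calculation.

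**From the documents:** two-sided testing with p < 0.05 (SAP 5.1); Fisher's exact test, which the SAP names for any TEAE and which is borrowed here because none is named for dermatological AEs; the filter in Protocol 5.10.

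**Assumed:**

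- n = 200 or 400 in each active arm, allocated equally.
- Share of subjects with any local reaction: 30% in one arm, 45% in the other.
- Share f of affected subjects whose reaction passes the filter: 10%, 25% or 50%, equal in both arms.
- No other dermatological AEs.

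**Formulas.** The AE rate in an arm is (share reacting) × f. Power is the sum, over all pairs (x, y), of Bin(x; n, p1) × Bin(y; n, p2), counting only pairs with two-sided Fisher p < 0.05.

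| Endpoint | Rates compared | Power, n = 200 | Power, n = 400 |
|---|---|---|---|
| Any reaction, unfiltered | 30% v 45% | 85.4% | 99.1% |
| AE, f = 50% | 0.30 × 0.50 = 15% v 0.45 × 0.50 = 22.5% | 43.4% | 75.2% |
| AE, f = 25% | 7.5% v 11.25% | 20.0% | 40.2% |
| AE, f = 10% | 3% v 4.5% | 7.4% | 15.5% |

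**Unequal pass shares.** Suppose 10% pass in the less irritating arm and 20% in the other. The rates are 0.30 × 0.10 = 3% v 0.45 × 0.20 = 9%, and power is 66.4% (n = 200) and 94.3% (n = 400).

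**Smaller difference.** The second set of assumptions is a true 10-point difference (10% v 20%, 15% v 25% or 20% v 30%), n = 200 to 600 per arm, equal f, and 0% or 1% of subjects with other dermatological AEs. The ranges of Fisher power are:

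| Endpoint | Power |
|---|---|
| Unfiltered | 60% to 99.8% |
| AE, f = 50% | 26% to 90% |
| AE, f = 25% | 12% to 58% |
| AE, f = 10% | 4% to 22% |

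The documents cannot fix f. Protocol section 7 gives 0.1% each for application site pain, exfoliation and irritation with the reference product, but not the recording rule behind those rates, so they do not calibrate the filter in 5.10.

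**The case against.** The strongest reply is that the plan uses two complementary streams. Reactions that led to action go into the AE data and the formal comparison. All seven signs are described at every visit in the ITT population, and a gap such as 30% v 45% would be visible there. Protocol and SAP agree on describing site reactions, and descriptive safety analysis is common practice. This stands as far as it goes: the trial as a whole is not blind to tolerability. It does not answer why the one formal skin comparison that the SAP commits to uses the less informative stream.

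Three stronger readings are tempting, and the documents do not support them.

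- *The filter removes most local reactions and leaves the test nearly blind.* No share is given. The first part is plausible, since a mild score is unlikely to trigger any of the three routes. Near-blindness needs a pass share of roughly 10% or less in both arms. At 50% the test is weakened only, and a more irritating gel may well have a higher pass share.
- *Subjects who leave because of irritation drop out of the later tables.* Protocol 5.17 says that the Visit 4/early-termination procedures should be completed after any discontinuation, so their scores may exist. What is missing is how the SAP places them. Protocol 5.10 also sends these subjects' reactions into the AE data.
- *Testing the scores would restore 85.4% or 99.1% power.* Those figures are for any reaction pooled over signs. Rates for a single sign, or for a score of 2 or more, would be lower, and no power has been worked out for them.

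Two further points stand. Tests on seven signs, unadjusted as SAP 5.1 provides, would carry up to 1 − 0.95^7 = 30% chance of at least one false positive if independent. And since safety text in the synopsis and Protocol 5.10 is blacked out, a further analysis cannot be excluded.

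**Conclusion.** The point holds as a weakness in the choice of analysis. In the visible text, the only formal skin-specific comparison of Test with Reference runs on AEs from which local reactions needing no action are excluded. The scored reactions get neither a per-subject summary nor a stated rule for early-termination and unscheduled scores.

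The formal comparison may therefore have reduced power for a tolerability difference. Under the 30% v 45% assumption with an equal pass share, the reduction runs from about half at a 50% pass share and 200 per arm (85.4% to 43.4%) to most of the power at a 10% pass share (85.4% to 7.4%). It is smaller if pass shares rise with irritation. Arm sizes, reaction rates, pass shares and the use of Fisher's test for this comparison are all assumptions. The mechanism does not depend on them; its size does. The change is worth making because it is cheap and uses data already collected.

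**What to change.** In SAP 5.6:

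1. For each of the seven signs, derive each ITT subject's worst post-baseline score over all visits, including early-termination and unscheduled visits. Tabulate it against the baseline score, since a sign such as erythema may be present before treatment.
2. Report the Test-minus-Reference difference in the proportion with a worst score of 2 or more, and in the proportion worsening from baseline, each with a 95% CI. Name this as the local-tolerability comparison.
3. If p-values are wanted, use a site-stratified CMH row-mean-score test, and label the results descriptive and unadjusted over seven signs.
4. Keep the by-visit tables and the dermatological AE comparison as supportive. For the latter, name the test and the term list, and state that reactions filtered by Protocol 5.10 are not in it.
5. Reconcile Protocol 5.10, Protocol 7.3 and SAP 5.6 on which local reactions enter the AE data, and Protocol 8.1.5 with the synopsis and SAP on dryness.

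The cost is SAP wording, a derived worst-score variable for each sign and a few more safety tables. No new data are needed. The downside is some chance findings across seven signs, which is why estimates with intervals should lead.
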